### SCHEDULE OF EVENTS

Day	Screening a	Cycle 1 and 2 Week 1	Weekly	Q 2 weeks	Q 4 weeks	End of Study b	Follow-up
Informed consent	X						
Demographics	X						
Inclusion/exclusion criteria	X						
Medical History	X	X					
Medication history	X						
Concomitant medications	X	X		X		X	
Physical examination	X	X		X		X	
ECOG performance status	X	X		X			
Vitals	X	X		X		X	
Height and weight c	X	X d				X	
CBC with differential	X	X	X			X	
Serum Chemistry	X	X	X			X	

panel e							
Direct Bilirubin	X		X				
Fibrinogen	X	X	X				
Serum or urine pregnancy test	X	X f					
Cardiac Ejection Fraction (MUGA/Echocardiogram)	X	x i					
Bone marrow biopsy/aspirate g	X				X	X	
Adverse Event Reporting	Recorded from the first dose of study drug through 30 days after last dose of study drug						
Survival h							X

a Screening procedures to occur up to 14 days before Cycle 1 Week 1 Visit, except for pregnancy test (within 7 days prior to Week 1 Visit).

b Perform end-of-study procedures 4 weeks after study completion or at time of early withdrawal. If study procedure cannot be performed on the scheduled day, the procedure must be performed within 48 hours.

c Height will be measured at Screening only.

d Weight will be checked on day 1 of every cycle

e Including albumin, total protein, total bilirubin, ALT, AST, LDH, alkaline phosphatase, bicarbonate, sodium, potassium, chloride, creatinine, BUN, and glucose.

f Serum  $\beta$ HCG pregnancy test in female patients of childbearing potential does not need to be repeated for Cycle 1 Week 1 Visit if the screening test was completed within 72 hours of Cycle 1 Week 1.

g Bone marrow aspirate and/or biopsy and cytogenetics must be performed within 4 weeks prior to Week 1 Visit. Bone marrow biopsies at week 4  $\pm$ 3 days

h Patients will be followed monthly until progression and then annually for survival.

i For cycle 2 only

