## **3. STUDY DESIGN**

In this phase I study, escalating doses of ixazomib will be combined with a fixed dose VXD regimen. Ixazomib will be administered on day 1, 8, and 15. If the patient experiences a DLT the dose of MLN maybe reduced to the next dose level on day 8 or day 15 in that patient. DLT would be any grade 3 or more toxicity which is

thought to be probably or definitely related to ixazomib. Three patients will be treated per dose level unless dose limiting toxicity (DLT) is observed. The starting dose of ixazomib will be 2.3 mg orally on days 1, 8 and 15. If toxicity is seen at this level then dose may be reduced to 1.5 mg (dose level -1). If no DLT is seen in the first 3 patients, the dose will be increased to 3 mg and then to 4 mg orally on days 1, 8 and 15 in a classic 3 +3 phase I design. The study will not attempt to increase the dose beyond 4 mg orally which, if achieved with acceptable toxicity, would be accepted as the recommended phase 2 dose (RP2D). 0 of 3 DLTs would allow escalation to the next dose level. 1 of 3 DLTs will require expanding to six patients; 1 of 6 DLTs will allow escalation again. Two DLTs will require dose de-escalation. Given that the liver toxicity with the VXLD + ixazomib was attributed to pegaspargase and it is eliminated from this protocol, we will start at dose level 1 of 2.3 mg. The maximum tolerated dose (MTD) will be the highest dose administered at which no more than 1 DLT was observed. All patients will be evaluated for hematopoietic stem cell transplantation. If patients achieve CR and are eligible for HSCT, they will proceed to HSCT. If they are not eligible, no donor is identified or if HSCT will be delayed, and the patient has achieved benefit, then treatment may be repeated at the discretion of the investigator. A total of 9-18 patients will be enrolled on the study. The study duration will be about 2 years. The DLT observation period will be from first dose of MLN9708 to 28 days after the first dose. Dose escalation to a higher dose level will require the last patient on the previous dose level to be out of the DLT observation period.

Patients will be offered an opportunity to provide samples to the institutional bank for use in future research.

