## **5. TREATMENT PLAN**

All patients will start therapy within 4 weeks from the bone marrow biopsy.

Lumbar puncture with intrathecal chemotherapy will be performed on all patients on day 1 (+/-1 day) to evaluate for disease.

BM or peripheral blood blast will be collected for correlative studies (optional) prior to starting therapy. Details of therapy are as follows:

Vincristine 1.5 mg/m^2 to a maximum dose of 2 mg IV on days 1, 8, 15 and 22

Dexamethasone 10 mg/m^2 orally or intravenously on days 1-14

Doxorubicin 60 mg/m^2 on day 1 by IV bolus.

For patients without CNS involvement:

-Cytarabine 100 mg will be administered intrathecally on day 1 (+/-1 day)  
(cytarabine dose should be reduced to 50 mg if given through a central ommaya reservoir)

-Methotrexate 12 mg will be administered intrathecally on day 8 (+/-1 day)

For patients with CNS involvement:

-Cytarabine 100 mg will be administered intrathecally on day 1 (+/-1 day)  
(cytarabine dose should be reduced to 50 mg if given through a central ommaya reservoir)

-Triple intrathecal chemotherapy with cytarabine 30 mg, methotrexate 15 mg and hydrocortisone 15 mg on (Day 8, 15 and 22 (+/-1 day)).

A bone marrow biopsy/aspirate will be performed at D28 +/- 3 days. For patients in remission, and have an available donor for HCT should proceed to HCT and be removed from the protocol treatment. Patients will still be followed for survival and progression free survival. A second cycle of treatment may be administered at the investigators discretion.

Ixazomib will be administered orally once weekly on day 1, 8 and 15. The first 3 patients will receive 2.3 mg orally (dose level 1). Dose escalation or de-escalation

will then proceed as previously detailed. There will be no inpatient dose escalation.

Table (7) Ixazomib dosing

	Day	Oral Dosing (mg)
Dose level -1	1, 8, 15	1.5
Dose level 1	1, 8, 15	2.3
Dose level 2	1, 8, 15	3
Dose level 3	1, 8, 15	4

Supportive care:

All patients will receive antibacterial, antiviral, antifungal and pneumocystis carinii pneumonia (PCP) prophylaxis. Prophylaxis regimen may follow institutional guidelines. The following prophylaxis may be used as guidelines:

Quinolones for antibacterial prophylaxis e.g., levofloxacin 500 mg orally daily

Antiviral prophylaxis: acyclovir 800 mg orally twice daily

Antifungal prophylaxis: Fluconazole 400 mg orally daily, or Liposomal Amphotericin B 9 mg/kg IV once per week or Caspofungin 50 mg IV /daily

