## **6.2 Study Drug Administration**

### Ixazomib Administration

All protocol-specific criteria for administration of study drug must be met and documented before drug administration. Study drug will be administered or dispensed only to eligible patients under the supervision of the investigator or identified subinvestigator(s). Patients should be monitored for toxicity, as necessary, and doses of ixazomib should be modified as needed to accommodate patient tolerance to treatment; this may include symptomatic treatment, dose interruptions, and adjustments of ixazomib dose (see Section 6.3).

Patients should be instructed to swallow ixazomib capsules whole, with water, and not to break, chew, or open the capsules. Study drug should be taken on an empty

stomach (no food or drink, except water) at least 1 hour before or 2 hours after a meal. Each capsule should be swallowed separately with a sip of water. Followed by 8 ounces (240 mL) of water.

Missed doses can be taken, as soon as the patient remembers, if the next scheduled dose is 72 hours or more away. A double dose should not be taken to make up for a missed dose. If the patient vomits after taking a dose, the patient should not repeat the dose but should resume dosing at the time of the next scheduled dose.

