## **13. TERMINATION OF TREATMENT AND/OR STUDY PARTICIPATION**

Patients will be informed that they have the right to withdraw from the study at any time for any reason, without prejudice to their medical care. The investigator also has the right to withdraw patients from the study for any of the following reasons:

- Adverse event
- Protocol violation
- Lost to follow-up
- Progressive disease
- Study terminated
- Other

At the time of withdrawal, all study procedures outlined for the End of Study visit should be completed. The primary reason for patient's withdrawal from the study should be recorded in the source documents and CRF.

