## **16. ADMINISTRATIVE REQUIREMENTS**

### **16.1 Data and Safety Monitoring**

The Medical College of Wisconsin Cancer Center Data Safety Monitoring Committee (DSMC) is responsible for monitoring data quality and subject safety for all cancer center investigator initiated clinical trials. A six to 8 member Data and Safety Monitoring Committee will complete a review of protocol-specific data safety monitoring reports, to provide recommendations on trial continuation, suspension or termination. The DSMC will review these reports no less than bi-annually. A summary of the DSMC activities are as follows

- Review the clinical trials for data integrity and safety
- Review all adverse events requiring expedited reporting as defined per protocol
- Review all DSM reports
- Submit a summary of any recommendations related to study conduct
- Terminate the study if deemed unsafe for patients

DSMC will review each new patient entry following induction. The study should not enroll any additional patients until the DSMC reviews the current patient report, and after the patient has completed the DLT observation period. The DLT observation period will be from first dose of MLN9708 to 28 days after the last dose. Dose escalation to a higher dose level will require the last patient on the previous dose level to be out of the DLT observation period.

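### The DLT observation period is defined in two conflicting ways, and the 3+3 counts have no DLT-evaluable definition or replacement rule

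*Combined protocol and SAP*

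**What the plan says.** Section 3 (Study Design) and the Protocol Summary set cohorts by patients treated: "Three patients will be treated per dose level unless dose limiting toxicity (DLT) is observed". They then apply the usual counts: 0 of 3 escalates, 1 of 3 expands to six, 1 of 6 escalates, and two DLTs de-escalate. The MTD is the highest dose given with no more than one DLT. A DLT is a toxicity of grade 3 or more judged probably or definitely related to ixazomib.

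The observation period appears twice. Section 3: "The DLT observation period will be from first dose of MLN9708 to 28 days after the first dose". Section 16.1: "The DLT observation period will be from first dose of MLN9708 to 28 days after the last dose". Both sections hold escalation until the last patient at a level is out of this period. Section 16.1 also holds each new enrolment "until the DSMC reviews the current patient report, and after the patient has completed the DLT observation period".

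Other sections foresee patients who are not followed or dosed as planned:
- Section 5, after the day-28 (±3 days) marrow: "For patients in remission, and have an available donor for HCT should proceed to HCT and be removed from the protocol treatment".
- Section 6.2: "If the patient vomits after taking a dose, the patient should not repeat the dose". A missed dose may be taken late only if the next one is at least 72 hours away.
- Section 13: "The investigator also has the right to withdraw patients from the study for any of the following reasons"; the list includes progression, protocol violation and loss to follow-up.

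The Schedule of Events has adverse events "Recorded from the first dose of study drug through 30 days after last dose of study drug", and Section 15.2 sets the same limit for serious events. Enrolment is given as 9-18 in the Protocol Summary and in Sections 3 and 14.1. Section 14.1, the whole statistical section, does not say who is counted.

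**The concern.** The MTD is the primary answer of the trial, and it is read directly from small counts of DLTs. Two things that fix those counts are unsettled.

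First, the window decides which toxicities count and when the next patient or dose level may open. With two end dates, the same patient with the same event in the disputed interval is a DLT under one section and not under the other.

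Second, the denominator is everyone treated. A patient who dies of leukemia, withdraws or is lost before the window closes, or who takes only part of the planned ixazomib, has not shown that the dose is tolerable. As written, that patient can still fill a place in a passing cohort. Section 16.1 requires completion of the window but gives no path when a patient cannot complete it. Without a rule set in advance, each such case is settled after its outcome is known.

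**Working it through.** **Plan's own figure.** Three planned levels × 3 patients = 9 and three × 6 = 18, so 9-18 reproduces.

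**Window dates.** Ixazomib is given on days 1, 8 and 15 (Section 5).
- Section 3: 1 + 28 = day 29.
- Section 16.1, full cycle: 15 + 28 = day 43, which is 14 days later.
- Transplant candidates leave protocol treatment after a marrow on days 25-31. That is 43 − 31 = 12 to 43 − 25 = 18 days before the longer window closes, but close to the end of the shorter one.
- A patient who takes only the day-1 dose reaches the end of both windows on day 29 with one third of the planned doses. Reconciling the windows therefore does not settle evaluability.

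**Acceptance of a dose.** Under the Section 3 rules a level with DLT rate p passes with probability

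A(p) = (1−p)³ + 3p(1−p)² × (1−p)³ = (1−p)³ + 3p(1−p)⁵.

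The documents give no DLT rate. Assume p = 0.40: A = 0.216 + 1.2 × 0.07776 = 0.309.

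**Effect of loss.** Assume a fraction q is lost before the window ends and counted as DLT-free. The worst-case bound has every loss preceding any DLT and no DSMC intervention, so the counted rate is p(1−q). If half of the lost patients' DLTs are seen first, it is p(1−q/2).

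| q | bound: rate → A | half seen: rate → A | at least one of 3 lost, 1−(1−q)³ |
|---|---|---|---|
| 5% | 0.380 → 34% | 0.390 → 33% | 14% |
| 9% | 0.364 → 37% | 0.382 → 34% | 25% |
| 20% | 0.320 → 45% | 0.360 → 38% | 49% |

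The 9% is for scale only. It is the 30-day death rate that Section 1.1 reports for another salvage regimen (8 of 88). Seven of those eight deaths were infectious, and a death judged related to ixazomib would itself be a DLT here.

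Over the whole escalation, with assumed rates of 20/30/40% at 2.3/3/4 mg, the chance of accepting 4 mg is 0.709 × 0.494 × 0.309 = 10.8%. It becomes 13/15/22% (bound) or 12/13/16% (half seen) at 5/9/20% loss.

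**Effect of the window.** Let s be the share of DLTs in the 14 days that only Section 16.1 counts. The answer depends on which window the 40% refers to, so both are shown.

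| s | 40% over longer window: Section 3 rate 0.4(1−s) → A | Section 16.1 A | 40% over shorter window: Section 3 A | Section 16.1 rate 0.4/(1−s) → A |
|---|---|---|---|---|
| 10% | 0.360 → 38% | 31% | 31% | 0.444 → 24% |
| 20% | 0.320 → 45% | 31% | 31% | 0.500 → 17% |
| 33% | 0.267 → 56% | 31% | 31% | 0.600 → 8% |

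The 33% row spreads DLTs evenly over 42 days (14/42). It is an extreme, because dosing stops on day 15 and a DLT must be attributed to ixazomib.

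**Timeline.** With one-at-a-time enrolment, the extra 14 days cost 9 × 14 = 126 to 18 × 14 = 252 days. For 18 patients the windows alone take 18 × 28 = 504 days or 18 × 42 = 756 days, against a study duration of about 2 years (Section 3).

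**Replacements.** Exact enumeration of the Section 3 rules with full cohorts gives 9.2-10.6 evaluable patients on average. The six assumed patterns (levels −1/1/2/3, in %) are 10/20/30/40, flat 10, flat 20, flat 30, 5/10/20/30 and 20/30/40/50. Expected replacements are this number × q/(1−q): with about 10 patients, 0.5, 1.0 and 2.5 at 5%, 9% and 20% loss.

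**The case against.** The best defence is that the gap is narrow in practice. A classic 3+3 is commonly understood to count evaluable patients. The DSMC looks at every patient. Adverse and serious adverse events are collected to 30 days after the last dose, which outlasts either window. Some missed doses can be recovered under the 72-hour rule. Much of this stands. It confines the counting problem mainly to death, withdrawal of consent, loss to follow-up and under-exposure, and the bias is small at low loss. But convention sets no exposure minimum or replacement rule. Collecting and reviewing data does not say who counts. The escalation rule in Section 3 can be met by elapsed time alone.

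Three stronger readings do not hold:
- A reader might infer that transplant patients go unobserved in the disputed interval. Section 5 removes them from protocol treatment, not from follow-up, and event collection continues. The difficulty is confounded attribution and the lack of a counting rule.
- A reader might infer that 9-18 is an error because some paths end earlier. The range is three levels of 3 to three levels of 6. Any other minimum depends on whether cohorts are completed after a second DLT and whether de-escalation triggers expansion. The range has no bearing on the validity of the MTD.
- A reader might infer that the shorter window is too lenient. That impression comes from fixing the 40% over the longer window; fixed over the shorter one, the longer window looks strict.

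**Conclusion.** The concern holds on two counts. The contradiction between Sections 3 and 16.1 is plain on the page, needs no assumption, and is not resolved elsewhere. It decides which events set the MTD and when enrolment and escalation may proceed. The missing evaluability and replacement rule is also real, and its direction is known: counting unobserved or under-exposed patients as DLT-free can only move the MTD upward.

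The sizes are conditional on assumed DLT, loss and timing rates. At a 40% DLT rate, early loss raises acceptance by 2 to 3 percentage points at 5% loss and by 7 to 14 points at 20%. The choice of window can shift it by about 7 to 14 points if 10-20% of DLTs fall in the disputed 14 days, and more only in the extreme case. The effect of under-exposure has not been quantified. The documents do not show which window was intended, and this point does not say which is right.

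**What to change.** 1. Reconcile the DLT observation period in Sections 3 and 16.1 into one definition. State how a patient removed for transplant inside that period is counted.
2. Apply the 3+3 counts to DLT-evaluable patients: those with a DLT, or those who completed the window with a pre-stated minimum cycle-1 ixazomib exposure. Keep in the count any patient whose doses were missed or held for ixazomib-related toxicity, so that the rule cannot remove toxicity from view.
3. Replace other non-evaluable patients, and have Section 16.1 say how enrolment continues after one.
4. Describe 9-18 in the Protocol Summary and Sections 3 and 14.1 as evaluable patients, plus replacements. If all three levels expand, 18 leaves no room for one.

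The cost is wording plus the replacements, on average about 0.5, 1.0 or 2.5 patients at 5%, 9% or 20% loss. Under one-at-a-time enrolment each replacement adds up to about 4 weeks with the shorter window or 6 with the longer, plus DSMC review. Keeping the longer window would be more than a wording change: about 14 days for every patient, which the stated study duration would have to absorb.

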C16014 Symptomatic MM N=701	PO, combination with LenDex	ixazomib 4.0 mg or matching placebo on Days 1, 8, and 15, plus Len 25 mg on Days 1-21 (10 mg if low creatinine clearance, with escalation to 15 mg if tolerated) and Dex 40 mg (or 20 mg if >75 years old) on Days 1, 8, 15, and 22
C16015 Symptomatic MM with normal renal function or severe renal impairment N=28	PO, combination with Dex	Part A: ixazomib 3.0 mg on Day 1 Part B: ixazomib 4.0 mg on Days 1, 8, and 15, plus Dex 40 mg (or 20 mg if >75 years old) on Days 1, 8, 15 and 22 of a 28-day cycle
C16017 RR follicular lymphoma N=58	PO, W	4.0, 5.3, and 7.0 mg, W Treatment at RP2D once determined.
C16018 Advanced solid tumors or hematologic malignancies with varying degrees of liver dysfunction N=45	Part A: PO, Day 1 of 15-day cycle Part B: PO, W	1.5 mg (severe hepatic impairment), 2.3 mg (moderate hepatic impairment), or 4.0 mg (normal hepatic function)
TB-MC010034 RRMM N = 10	PO, W	4.0 mg, W Single agent: 4.0 mg Combination with Rd

Abbreviations: RRAL = Relapsed and/or refractory Primary systemic light chain (AL) amyloidosis; BSA = body surface area; Dex=dexamethasone; DLT = dose-limiting toxicity; IV = intravenously; LenDex = lenalidomide plus dexamethasone; MTD = maximum tolerated dose; NDMM = newly diagnosed multiple myeloma; PO = orally; RR= relapsed and/or refractory; RRAL= relapsed and/or refractory systemic light chain amyloidosis RRMM = relapsed and/or refractory multiple myeloma; TBD = to be determined; TW = twice weekly; W = weekly; RP2D= recommended phase 2 dose.

Note that blinded data from pivotal Studies C16010 and C16011 are not included.

a Approximate BSA and fixed dosing equivalence: 3 mg~ equivalent to 1.68 mg/m^2 BSA dosing; 4.0 mg ~ equivalent to 2.23 mg/m^2 BSA dosing; and 5.5 mg~ equivalent to 2.97 mg/m^2 BSA dosing.

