## **2. STUDY OBJECTIVES**

### **2.1 Primary Objectives**

The primary objective is to determine the maximum tolerated dose of IXAZOMIB with VXD and to assess the tolerability of VXD + ixazomib in adult patients with relapsed refractory acute lymphocytic leukemia/lymphoma, lymphoblastic lymphoma or mixed phenotype acute leukemia

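### If 4 mg is reached with no more than one DLT, the protocol names it the MTD, although no higher dose is tested and no limiting dose has been found

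*Combined protocol and SAP*

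**What the plan says.** Section 2.1 sets the aim: "The primary objective is to determine the maximum tolerated dose of IXAZOMIB with VXD", together with assessing tolerability. Section 3 and the overview in the Protocol Summary give the rules.

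- **Escalation:** a level clears when none of its three patients has a DLT. When one of them does, the rule is "1 of 3 DLTs will require expanding to six patients; 1 of 6 DLTs will allow escalation again".
- **De-escalation, as worded in Section 3:** "Two DLTs will require dose de-escalation".
- **Cap:** "The study will not attempt to increase the dose beyond 4 mg orally". If 4 mg proves acceptably tolerable, it is taken as the recommended phase 2 dose (RP2D). Table (7) in Section 5 lists no level above 4 mg.
- **MTD:** "The maximum tolerated dose (MTD) will be the highest dose administered at which no more than 1 DLT was observed".

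Section 14.1 repeats the escalation scheme and the total of 9-18 patients. It adds no MTD rule. No section provides for an MTD that is not reached.

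**The concern.** A 3+3 design locates an MTD by finding a dose that fails and naming the one below it. Here the definition needs only the lower half of that evidence. When the highest planned dose passes, the definition is met with nothing above it to mark a limit.

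Two different results then carry the same label. One is a dose with observed toxicity at the level above. The other is the highest dose the sponsor chose to test. The label answers the primary objective, so the trial's main conclusion could state a toxicity limit that the trial did not find, and someone who sees only the headline could not tell which case applied.

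**Working it through.** **1. The plan's own figure.** There are three planned levels (2.3, 3 and 4 mg). With 3 patients each, 3 × 3 = 9; with 6 each, 3 × 6 = 18. This reproduces the stated 9-18. The lower end is the path 0/3, 0/3, 0/3. The whole trial then has no DLT, and the definition still names 4 mg the MTD.

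**2. The definition applied to two results.**

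| Result | Dose named MTD | Evidence above it |
|---|---|---|
| 3 mg passes, 4 mg has 2 DLTs | 3 mg | Next level met the de-escalation rule |
| 4 mg has 0/3 or 1/6 DLTs | 4 mg | None; no higher level exists |

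**3. How the protocol uses the term elsewhere.** Every study in Table 1-1 (Section 1.6) that lists an MTD also tested a dose above it:

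- C16003: up to 2.23 mg/m², MTD 2.0 mg/m²
- C16004 and C16005: up to 3.95 mg/m², MTD 2.97 mg/m²
- C16006: up to 3.7 mg (Arm A) and 5.5 mg (Arm B), MTD 3.0 mg
- C16007: up to 5.5 mg, MTD 4 mg
- C16008: up to 3.7 mg, MTD 3.0 mg

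The Summary takes the 4 mg cap from the RP2D of the lenalidomide-dexamethasone combination (2.23 mg/m²), which is below the MTD of that combination (2.97 mg/m²). A dose brought in as an RP2D could leave this trial labelled an MTD.

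**4. How often this could happen.** The protocol states no DLT rate and no target rate, so the rates p below are assumptions. A level passes with 0/3, or with 1/3 followed by 0/3:

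P(pass) = (1−p)³ + 3p(1−p)² × (1−p)³ = (1−p)³ + 3p(1−p)⁵

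With the same p at all three levels, the chance that 4 mg is named the MTD is P(pass)³.

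| Assumed p | P(pass) | P(pass)³ |
|---|---|---|
| 5% | 0.857 + 0.116 = 0.973 | 0.92 |
| 10% | 0.729 + 0.177 = 0.906 | 0.74 |
| 16.7% | 0.579 + 0.201 = 0.780 | 0.47 |
| 25% | 0.422 + 0.178 = 0.600 | 0.22 |
| 33% | 0.301 + 0.134 = 0.434 | 0.08 |

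With rates that rise across the levels, the product of the three pass probabilities is 0.72 for 5/10/15%, 0.62 for 5/10/20% and 0.28 for 10/20/33%.

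**5. What such a result shows about 4 mg.** With 0/3, the exact one-sided 95% upper limit for the DLT rate is 1 − 0.05^(1/3) = 63.2%. With 1/6 it is 58.2%. A true rate of 33% gives 0/3 in 0.67³ = 30% of cohorts. Passing at 4 mg therefore says little about whether the true MTD lies below, at or above 4 mg.

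**The case against.** The strongest reply is that the protocol already labels this outcome. The paragraph that defines the MTD also says that 4 mg, if achieved with acceptable toxicity, becomes the RP2D. That is the dose carried forward, and nothing here changes it. Section 14.1 summarises adverse events by dose level, so the data behind 4 mg should be visible. Tolerability is also part of the primary objective and is unaffected by the cap.

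Much of this stands. No dose, escalation decision or sample size turns on the point. But the RP2D sentence does not replace the MTD sentence: both apply at 4 mg, and only the MTD answers the first half of the primary objective. Capping a 3+3 is a legitimate choice and is not at issue here.

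A reader might infer that the protocol's own data make this outcome likely, because Table 1-1 lists a weekly MTD of 2.97 mg/m² in C16004 and C16005 and its footnote reads "and 5.5 mg~ equivalent to 2.97" mg/m². The documents do not support that. Both are myeloma studies without VXD. C16006, with melphalan and prednisone, lists 3.0 mg, and C16007 lists 4 mg. Section 3 also counts any grade 3 or higher toxicity probably or definitely related to ixazomib, with no written haematological exemption, while Section 7.1 expects neutropenia and/or thrombocytopenia in all patients. No DLT rate for this combination can be read from these sources.

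**Conclusion.** The point holds, conditionally. If 2.3 mg and 3 mg clear and 4 mg has 0/3 or 1/6 DLTs, the stated rule gives a primary conclusion that the design cannot support. This follows from the text and needs no assumption. Only the chance of the outcome depends on assumptions: about 0.92 to 0.08 for flat DLT rates of 5% to 33% per level, with the escalation rules followed as written. It is plausible, and it cannot be called likely.

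A reader might also infer that passing at 4 mg shows the true MTD to be higher. It does not. In this setting, not reached means only that no tested dose met the de-escalation rule, and the upper limits of 63.2% (0/3) and 58.2% (1/6) show how little else is known.

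That the label may rest on three patients is a separate matter of cohort size at the top level, which the change below does not resolve.

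**What to change.** Amend the MTD sentence in Section 3 and in the Summary overview along these lines: *An MTD is declared only when the next higher tested level had 2 or more DLTs. If the top planned level is completed with no more than 1 DLT, the result is reported as MTD not reached; maximum administered dose 4 mg, with the number treated and the DLTs observed at that level.*

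Reword the primary objective in Section 2.1 and the Summary to: *determine the MTD or, if not reached, the RP2D within the planned dose range*. The assessment of tolerability stays as it is.

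The cap, the dose levels, the total of 9-18 patients and the protocol's own RP2D sentence are unchanged. The cost is an amendment of wording and a less definite headline conclusion if 4 mg passes.
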